## **12 Data analysis and statistical methods**

The data will be analyzed by Novartis and/or a designated CRO. Any data analysis carried out independently by the investigator should be submitted to Novartis before publication or presentation.

Data from all participating centers will be combined, so that an adequate number of patients will be available for analysis. The primary analysis of the study will be performed after all patients have completed the Month 12 visit or prematurely discontinued the study. For this analysis, all primary, secondary [REDACTED] objectives will be addressed including all variables outlined up to Month 12 and all available safety data. A final Clinical Study Report (CSR) will be produced for the primary analysis of the study.

As required, interim analyses may be performed every six months annually for publication purpose.

### **12.1 Analysis sets**

The analysis sets to be used are defined as below. The Full Analysis Set (FAS) will be used as the primary efficacy analysis set. The Safety Set will be used for all the safety analyses.

All tables and listings will be presented by one treatment arm of CTL019.

#### **12.1.1 Screened Set**

The Screened Set comprises all patients who have signed informed consent/assent and screened in the study.

#### **12.1.2 Enrolled Set**

The enrolled set (ENS) comprises all patients who are enrolled in the study. Enrollment is defined as the point at which the patient meets all inclusion/exclusion criteria, and the patients' additional non-expired dose of tisagenlecleucel has been confirmed available.

#### **12.1.3 Full Analysis Set**

The Full Analysis Set FAS comprises all patients whom have received reinfusion of tisagenlecleucel.

#### **12.1.4 Safety Set**

The Safety Set comprises all patients who received re-infusion of tisagenlecleucel.

### **12.1.5 Per-Protocol Set**

The Per-Protocol Set (PPS) consists of a subset of the patients in the FAS who are compliant with major requirements of the clinical study protocol (CSP).

Detailed criteria and determination of major protocol deviations leading to exclusion from PPS will be finalized prior to database lock and primary analysis.

### **12.1.6 Cellular kinetic analysis set**

The Cellular Kinetic Analysis Set (CKAS) consists of all subjects in the FAS who provide evaluable tisagenlecleucel cellular kinetic data. A subject is considered as having evaluable cellular kinetic data if at least one cellular kinetic parameter can be derived. The CKAS will be used for summaries (tables and figures). The FAS will be used for listings of cellular kinetic data.

Note that subjects will be removed from the estimation of certain CK parameters on an individual basis depending on the number of available samples. These subjects will be identified at the time of the analyses.

### **12.1.7 Pharmacokinetic analyses set**

The Pharmacokinetic Analysis Set (PKAS) consists of subjects in FAS who have taken at least one dose of the drug and provided at least one PK concentration.

## **12.2 Subject demographics and other baseline characteristics**

Demographic and other baseline data will be listed by patient and/or summarized descriptively for the FAS.

Categorical data will be presented as frequencies and percentages. For continuous data, summary statistics will be presented (i.e., mean, median, standard deviation (SD), minimum, maximum).

The number and percentage of patients with prior anti-neoplastic medications/therapies will be summarized.

Relevant medical histories and current medical conditions at baseline will be summarized by primary system organ class (SOC) and preferred term.

## **12.3 Treatments**

The Safety Set will be used for the analyses below. Categorical data will be summarized as frequencies and percentages. For continuous data, mean, SD, median, minimum, and maximum will be presented.

The total cells infused (cells/kg) and total CTL019 transduced viable T cells infused (cells/kg) will be listed and summarized using descriptive statistics. Patients will be categorized as below, within or above the prescribed dose range.

Prior and concomitant medications and significant non-drug therapies prior to and after the start of re-infusion will be listed by patient and summarized by the Anatomical Therapeutic

Chemical (ATC) term.

**12.4 Transfusion during the study will be listed. In addition, whether patients have received anti-cytokine medications for the management of CRS will be summarized. Analysis of the primary endpoint(s)**

The primary objective of the study is to evaluate the incidence of B cell aplasia after re-infusion of tisagenlecleucel.

**12.4.1 Definition of primary endpoint(s)**

The primary endpoint for this study is the proportion of patients who restore B-cell aplasia within 12 months following re-infusion with tisagenlecleucel.

B-cell aplasia is defined as:

- PB absolute B lymphocyte count  $< 50/\mu\text{L}$ , AND
- presence of CTL019 cells by qPCR in the peripheral blood

**12.4.2 Statistical model, hypothesis, and method of analysis**

The primary efficacy analysis will be performed on the FAS by testing the following hypothesis:

$$H_0: p \leq 0.10 \text{ vs. } H_A: p > 0.10$$

The estimated proportion  $\hat{p}$  of patients who restore B-cell aplasia within 12 months following re-infusion with the study drug will be presented together with an exact 95% Clopper-Pearson confidence interval (CI).

The null hypothesis ( $H_0$ ) will be rejected if the lower limit of the 95% CI is greater than 0.10, demonstrating improvement after re-infusion.

**12.4.3 Handling of missing values/censoring/discontinuations**

Patients in the study who are of unknown clinical response will be treated as non-responders. Other missing data are simply noted as missing on appropriate tables/listings.

Patients who proceed to HSCT while in remission after tisagenlecleucel re-infusion will be censored at the time of HSCT.

The volume of missing data generated due to the COVID-19 pandemic may also be assessed and sensitivity analyses will be performed, if deemed appropriate.

**12.4.4 Sensitivity and Supportive analyses**

In order to assess the robustness of the primary endpoint, sensitivity analyses are planned. These may include, but are not limited to:

- the analysis of the primary endpoint using the PPS
- the analysis of the primary endpoint without censoring for HSCT

As this study is ongoing during the COVID-19 pandemic, the impact of COVID-19 (if any) will be explored on topics such as, but are not limited to, the discontinuation rate, the number of

protocol deviations, disease status, the use of rescue medications, AEs, laboratory values and missing data. As appropriate, a sensitivity analysis of the primary endpoint may be performed to assess the impact of COVID-19, if any, in the study.

#### **12.4.4.1 Subgroup analysis**

Subgroup analyses will be performed on the primary endpoint based on the patient's baseline status:

- Age: <10 years,  $\geq$ 10 years to <18 years,  $\geq$ 18 years
- Gender: Male, Female
- Race: White, Asian, Other
- Patients with a loss of B-cell Aplasia within 9 months of first infusion AND are MRD (+) at time of enrollment
- Patients with a loss of B cell aplasia very early (<3 months), early (>3 to <6 months) and late (>6 months) following first infusion

As the sample size is small, data will be only summarized within each subgroup.

### **12.5 Analysis of secondary endpoints**

- The secondary efficacy objectives are to evaluate the following: the efficacy of reinfusion of tisagenlecleucel for loss of B cell aplasia as measured by overall remission rate (ORR) 12 months after tisagenlecleucel reinfusion, which includes CR and CR with incomplete blood count recovery (CRi) as determined by investigator assessment for pALL patients Evaluate event free survival (EFS)
- Evaluate Overall survival (OS)

#### **12.5.1 Overall Remission rate (ORR)**

The secondary endpoint is the ORR as determined by investigators assessment during the 12 months after tisagenlecleucel re-infusion. The ORR is defined as the proportion of patients who maintain ORR (= CR + CRi) per Investigator assessment in pALL patients during 12 months post-reinfusion.

The secondary efficacy endpoint, ORR within 12 months of re-infusion, will be analyzed using the FAS. The ORR will be summarized and exact 95% Clopper-Pearson CIs will be reported.

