1.2 Study objectives and endpoints

Objectives and related endpoints are provided in [Table 1-1](#).

Table 1-1 Study objectives and endpoints

| Objectives | Endpoints |
|---|---|
| Primary Objective | Endpoint for primary objective |
| 
Evaluate the incidence of B-cell aplasia after re-infusion of tisagenlecleucel | 
Proportion of patients who establish B-cell aplasia within 12 months of re-infusion, as measured by circulating B lymphocytes (< 50/μL) in the peripheral blood. |
| Secondary Objectives | Endpoints for secondary objectives |
| 
Evaluate the efficacy of re-infusion of tisagenlecleucel for loss of B-cell aplasia as measured by Overall Remission Rate (ORR) 12 months after tisagenlecleucel re-infusion, which includes complete remission (CR) and CR with incomplete blood count recovery (CRI) as determined by investigator assessment for pALL patientsEvaluate Event Free Survival (EFS)Evaluate Overall Survival (OS) | 
Proportion of patients with ORR (= CR + CRI) per Investigator assessment in pALL patients during 12 months post re-infusion.EFS, i.e. the time from date of tisagenlecleucel re-infusion to the earliest of relapse, treatment failure or deathOS, i.e. the time from date of tisagenlecleucel re-infusion to the date of death due to any reason |

| Objectives | Endpoints |
|---|---|
| 
Evaluate the safety of tisagenlecleucel re-infusion therapy | 
Safety parameters including adverse events (AEs) and laboratory abnormalities |

2 Statistical methods

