2.1 Data analysis general information

This study will be conducted under the sponsorship of Novartis.

The analysis outlined in this document will be performed by Novartis or a designated contract research organization (CRO) (if applicable). SAS® version 9.4 or higher will be used for generating tables, figures, and listings (TFLs). It is planned that the data from all participating centers will be used.

Data will be listed for all patients with respect to demographic and baseline characteristics, efficacy, and safety observations and measurements.

All data will be listed by center, patient number and one treatment arm of the tisagenlecleucel (tisagenlecleucel is as defined in [Section 2.1.1.1](#)), unless stated otherwise.

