2.3.3.2 ALL characteristics

The following ALL disease characteristics at Baseline will be listed

- Evidence of extramedullary involvement (Yes, No)
- CD19 status (Positive, Negative, Not Done, Unknown)
- Overall minimal residual disease (MRD) status (Positive, Negative, Not Done, Unknown)
- MRD biomarker analyte and associated phenotype result (%)

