2.6 Analysis of the primary objective

The primary objective of the study is to evaluate the efficacy of re-infusion of tisagenlecleucel for restoring B-cell aplasia as measured by the incidence of B-cell aplasia within 12 months following tisagenlecleucel re-infusion.

Where **loss of B-cell aplasia** (i.e. B-cell recovery) is defined as:

- PB absolute B lymphocyte count $\geq 50/\mu\text{L}$, OR
- Peripheral blood B lymphocyte $\geq 10\%$ of the total lymphocytes

And where **B-cell aplasia** is defined as:

- PB absolute B lymphocyte count $< 50/\mu\text{L}$

The primary analysis of the study was to be performed after all patients had completed the 12-month follow-up period or discontinued earlier. However, this study terminated early due a very low rate of enrollment, and only 5 out of a planned 54 patients were enrolled; the low sample size provides insufficient data to perform the planned statistical analyses (see [Section 4](#)). Therefore, the available study data will be listed only for the primary objective using Full Analysis Set.

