2.8 Analysis of secondary efficacy objectives

Note: The secondary efficacy analysis will not be performed as there is an inadequate number of patients in the study.

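### Do the conflicting definitions of overall remission rate, with no named remission status at entry, need correcting now that the ORR analysis is cancelled?

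*Protocol*

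**What the plan says.** Protocol 12.5.1 first states that "The ORR is defined as the proportion of patients who maintain ORR", meaning CR plus CRi by investigator assessment, during the 12 months after re-infusion. Its next paragraph reads "The secondary efficacy endpoint, ORR within 12 months of re-infusion, will be analyzed using the FAS". The objective in Protocol 12.5 describes efficacy "as measured by overall remission rate (ORR) 12 months after tisagenlecleucel reinfusion". The endpoint row in SAP Table 1-1, which matches Protocol Table 2-1, is "Proportion of patients with ORR (= CR + CRI) per Investigator assessment in pALL patients during 12 months post re-infusion".

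The inclusion criteria in Protocol 5.1 require CD19-positive leukemia and B-cell recovery, and neither require nor exclude remission. Protocol 4.5 foresees patients with and without overt relapse. The baseline lists in Protocol 8.2.2 and SAP 2.3.3 name MRD status but have no item for CR, CRi or relapse at entry. Protocol 8.3.1 refers to Appendix 1 for the response criteria, and Appendix 1 is about hepatitis serology.

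SAP Amendment 2 was issued after the decision to close the trial. It records in Section 2.6 that "only 5 out of a planned 54 patients were enrolled". Section 2.8 says "The secondary efficacy analysis will not be performed as there is an inadequate number of patients in the study", and Section 2.1 says "Data will be listed for all patients with respect to demographic and baseline characteristics, efficacy, and safety observations and measurements".

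**The concern.** Re-infusion here is meant partly to prolong an existing remission, so some patients would be expected to enter in CR or CRi. Such a patient counts as a responder at once if ORR means ever in remission within 12 months, whatever re-infusion does. The same patient counts only if the remission lasts when ORR means maintained, or present at Month 12. The Full Analysis Set pools everyone re-infused, so a single ORR would mix carried-over remissions with new ones.

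Marrow after Day 28 is optional, so late status may be thinly documented, and the response criteria cannot be found where Protocol 8.3.1 places them. If an ORR were going to be estimated, these points together could leave the figure without a clear meaning. With five patients, the worry becomes that a reader of the listing might take a remission that predates re-infusion for a response to it.

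**Working it through.** **1. Is there a planned figure to reproduce?** No. Neither document gives a target, power or sample size for ORR. The 49 evaluable and 54 enrolled patients in Protocol 12.8 and SAP Section 3 belong to the B-cell aplasia endpoint.

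**2. How far apart are the readings in principle?** Let *s* be the share in remission at entry, *r* the chance of a new remission if not in remission, and *k* the chance that a remission lasts to Month 12, taken as equal for old and new remissions.

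- Ever in remission: s + (1 − s)r
- In remission at Month 12: [s + (1 − s)r]k
- Entry remission maintained: s × k

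The documents do not give *s*. For *r*, the range runs from 1/3 (one of three children re-infused for CD19-positive relapse, Protocol 1.2) to 0.81 (first infusion, Protocol 1.1.5.1). For *k*, it runs from 0.59 (12-month relapse-free survival after first infusion, Protocol 1.1.5.1) to 6/7 = 0.857 (Protocol 1.2, timed from the initial infusion). None of these was measured in this setting, so all are assumptions.

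| Reading | s = 0.5 | s = 1 |
|---|---|---|
| Ever | 0.5 + 0.5 × 1/3 = 0.667 to 0.5 + 0.5 × 0.81 = 0.905 | 1.00 |
| At Month 12 | 0.667 × 0.59 = 0.393 to 0.905 × 0.857 = 0.776 | 0.59 to 0.857 |
| Maintained | 0.5 × 0.59 = 0.295 to 0.5 × 0.857 = 0.429 | 0.59 to 0.857 |

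The wording would therefore have mattered in a full trial. The table illustrates that and does not measure an error in the present plan: *s* is free, and the value 1.00 is true by construction.

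**3. What does the current SAP produce for ORR?** No proportion and no interval. Sections 2.8, 2.8.1 and 2.8.1.1 each say that the secondary efficacy analysis will not be performed. With five re-infused patients, one reclassification would move 5/5 (exact 95% CI 48 to 100%) to 4/5 (28 to 99%), a shift of 20 points, but neither figure is a planned output. Five is also the number enrolled. The number re-infused, which defines the Full Analysis Set, is not stated and is at most five.

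**4. Can entry status be read from the listings?**

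- Protocol Table 8-1 requires marrow, hematology and chemistry at screening, all recorded in the database.
- SAP 2.3.3.2 lists extramedullary involvement, CD19 status, MRD status and the MRD percentage.
- SAP 2.3.3.5 lists prior anti-neoplastic therapy, SAP 2.3.5 lists all other baseline data, and SAP 2.9.2 lists laboratory data.
- SAP Section 4 lists all study data.

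A patient who is MRD-negative with no extramedullary disease is readily placed. An MRD result that is positive, not done or unknown leaves the question to the marrow and blood counts. Inference is often possible, though not guaranteed.

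**5. Does the lack of a later marrow turn a remission into a failure?** The documents do not say so. ORR rests on investigator assessment. Blood counts, physical examination, extramedullary assessment and CNS symptom review continue at Months 3, 6 and 12, with marrow if clinically indicated. The rule that counts unknown response as non-response is in Protocol 12.4.3, under the primary endpoint, and the matching SAP 2.6.3 is now marked not applicable.

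**The case for a change.** The strongest case for acting is that with so few patients the listing is the efficacy evidence. Results are to be posted publicly (Protocol 13.3), and SAP Table 1-1 still carries two time references, 12 months after in the objective and during 12 months in the endpoint. One stated definition and a column for remission status at screening would cost almost nothing, need no new visits, and stop a carried-over remission being credited to re-infusion.

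Much of this stands as description. Protocol 12.5.1 does contradict itself, entry remission status is not a named item, MRD status alone does not separate morphologic remission from relapse, and the Appendix 1 reference is wrong. It does not show that a planned result would differ. The outlying verb, *maintain*, is absent from the SAP. *During* and *within* 12 months can be read alike, and the endpoint rows of both documents say *during*. A medical writer describing a handful of patients would state disease status before re-infusion as a matter of course.

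A larger remedy, splitting ORR into remissions gained and remissions kept, would define new endpoints after the decision to close an open-label trial. It would also divide at most five patients, some of whom may not have reached Month 12 before closure. That is harder to defend than leaving the endpoint alone.

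**Conclusion.** The inconsistency is real, but no change to the plan follows. The effect on planned estimates, intervals and tests is nil, because the current SAP produces none for ORR. The residual effect is on how a listing of at most five re-infused patients is read, where entry status may have to be inferred from screening data instead of being read from a labelled column. That is missing detail that analysts and report writers can fill, and the appendix reference is a clerical slip.

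This rests on two assumptions: that the SAP's listing-only plan stands and no ORR proportion is tabulated later, and that the screening marrow and MRD results were recorded as Protocol Table 8-1 requires. Had the trial run to 54 patients with ORR estimated, one definition and a rule for patients entering in remission would have been needed.

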#### **12.5.2 Event free survival (EFS)**

EFS is the time from date of tisagenlecleucel re-infusion to the earliest of the following:

- Death from any cause after remission
- Relapse
- Treatment failure: Defined as no response in the study and discontinuation from the study due to any of the following reasons:
  - Death
  - Adverse event (including abnormal laboratory values or abnormal test procedure
  - results)

- Lack of efficacy or progressive disease
- New anticancer therapy

In the main analysis of EFS, patients who proceed to SCT after tisagenlecleucel re-infusion will be censored at the time of SCT. In addition, a sensitivity analysis of EFS will be performed without censoring SCT. EFS will be assessed in all patients in the FAS. The distribution function of EFS will be estimated using the Kaplan Meier (KM) method. The median EFS along with 95% confidence intervals will be presented, if appropriate.

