## 2 Objectives and endpoints

**Table 2-1 Objectives and related endpoints**

Objective(s)	Endpoint(s)
Primary Objective(s)	Endpoint(s) for primary objective(s)

• Evaluate the incidence of B cell aplasia after reinfusion of tisagenlecleucel

	

• Proportion of patients who establish B cell aplasia within 12 months of reinfusion, as measured by circulating B lymphocytes (< 50/<math>\mu</math>L) and presence of CTL019 cells by qPCR in the peripheral blood.

Secondary Objective(s)	Endpoint(s) for secondary objective(s)

Objective(s)	Endpoint(s)

Evaluate the efficacy of reinfusion of tisagenlecleucel for loss of B cell aplasia as measured by overall remission rate (ORR) 12 months after tisagenlecleucel reinfusion, which includes CR and CR with incomplete blood count recovery (CRI) as determined by investigator assessment for pALL patients

Evaluate event free survival (EFS)

Evaluate Overall survival (OS)

Evaluate the safety of tisagenlecleucel reinfusion therapy

	

Proportion of patients with ORR (= CR + CRI) per Investigator assessment in pALL patients during 12 months post-reinfusion

EFS, i.e. the time from date of tisagenlecleucel reinfusion to the earliest of relapse, treatment failure, or death

OS, i.e. the time from date of tisagenlecleucel re-infusion to the date of death due to any reason

Safety parameters including adverse events and laboratory abnormalities

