### **9 Study discontinuation and completion**

#### **9.1 Discontinuation**

##### **9.1.1 Discontinuation of study**

Patient's participation in the study may be discontinued if, in the investigator's opinion, its continuation would be detrimental to the patient's safety.

Subjects who discontinue from study should NOT be considered withdrawn from the study before they return for the EOS assessments indicated in [Section 9.2 Study completion and post-study treatment](#). If they fail to return for these assessments, every effort (e.g. telephone, email, letter, etc.) should be made to contact them.

Discontinuation of study for a subject occurs when study is stopped earlier than the protocol planned duration, and can be initiated by either the subject or the investigator.

Study participation must be discontinued under the following circumstances

- Subject/guardian decision
- Investigator Decision
- Pregnancy
- Use of prohibited treatment as per recommendations in [section 6.2.2](#)
- Any situation in which study participation might result in a safety risk to the subject
- Any laboratory abnormalities that in the judgment of the investigator, prevents the subject from continuing participation in the study

If discontinuation occurs, the investigator should make a reasonable effort to understand the primary reason for the subject's premature discontinuation of study and record this information.

Subjects who discontinue the study or who decide they do not wish to participate in the study further should NOT be considered withdrawn from the study UNLESS they withdraw their consent (see [section 9.1.2/Withdraw of informed consent section](#)). **Where possible, they should return for the assessments indicated** in the assessment schedule. If they fail to return for these assessments for unknown reasons, every effort (e.g. telephone, e-mail, letter) should be made to contact the subject/pre-designated contact as specified in the lost to follow-up section. This contact should preferably be done according to the study visit schedule.

If the subject cannot or is unwilling to attend any visit(s), the site staff should maintain regular telephone contact with the subject, or with a person pre-designated by the subject. This telephone contact should preferably be done according to the study visit schedule.

If the subject is willing, at a minimum, in abbreviated visits, the following data should be collected at clinic visits or via telephone/email contact:

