### **12.5.3 Overall survival (OS)**

OS is the time from date of tisagenlecleucel re-infusion to the date of death due to any reason. In case a patient is alive at the date of last contact on or before data cut-off, OS is censored at the date of last contact. No censoring will be done in case of SCT. Thus, patients should be followed-up for survival also in case of SCT.

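### Does the EFS definition let a non-responder who stays on study count as event-free, and does that call for a change?

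*Protocol*

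**What the plan says.** Table 2-1 of the protocol gives the short form: "EFS, i.e. the time from date of tisagenlecleucel reinfusion to the earliest of relapse, treatment failure, or death". Treatment failure is not defined there, nor in the matching SAP Table 1-1.

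Protocol 12.5.2 gives the long form, with three kinds of event:
- "Death from any cause after remission";
- relapse;
- treatment failure, where "Treatment failure: Defined as no response in the study and discontinuation from the study due to any of the following reasons" introduces four reasons: death, adverse event, "Lack of efficacy or progressive disease" and "New anticancer therapy".

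In the main analysis, "patients who proceed to SCT after tisagenlecleucel re-infusion will be censored at the time of SCT"; a sensitivity analysis leaves out that censoring. The section states no date for a treatment failure and no other censoring rule.

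Protocol 9.1.1 has its own list, opened by "Study participation must be discontinued under the following circumstances". It names subject or guardian decision, investigator decision, pregnancy, prohibited treatment, safety risk and laboratory abnormalities. It does not name lack of efficacy, progression or new anticancer therapy. It also tells the investigator to find out and record the main reason for leaving.

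SAP Amendment 2 was issued after the decision to close the trial. Section 2.1.1.10 marks time-to-event definitions as not applicable. Sections 2.8, 2.8.1 and 2.8.1.1 say the secondary efficacy analysis will not be done. Sections 2.6 and 4 give 5 patients enrolled out of 54 planned, with study data to be listed.

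**The concern.** The treatment is a single commercial infusion, so leaving the study says little about whether it worked. A failure definition that requires departure ties the event to an administrative step rather than to the disease. A non-responder cannot relapse, because relapse presupposes remission. While alive and on study, such a patient meets none of the three event types and would presumably be censored at the last assessment.

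The protocol makes this possible. Section 8.1.6 follows patients for a year regardless of response. Section 6.2.2 bars investigational therapy on study only until first progression, so it expects some patients to remain afterwards. Section 4.5 discusses re-infusion in overt relapse, so patients with active disease can be in the trial. The error would run in one direction, towards better EFS. New non-transplant therapy in a responder is also neither an event nor a censoring point.

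**Working it through.** **1. The plan's own figure.** The documents state no EFS rate, event count or power. The only planned figure is the sample size in Protocol 12.8 and SAP 3, which rests on B-cell aplasia. It reproduces. With an exact binomial test, p0 = 0.10, p1 = 0.25 and one-sided alpha 0.025, n = 49 rejects at 10 or more responders, with exact alpha 0.0215 and power 0.817; n = 48 gives power 0.795. Dropout: 49 / 0.90 = 54.4, against a stated approximate 54. None of this uses EFS.

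**2. Who falls through the definition.**

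| Patient after re-infusion | Treatment under Protocol 12.5.2 |
|---|---|
| In remission, later relapses | Event (relapse) |
| In remission, dies | Event (death after remission) |
| Never responds, dies | Event (failure, listed reason is death) |
| Never responds, leaves with a listed reason recorded | Event (failure) |
| Goes to transplant | Censored at transplant; not censored in the sensitivity analysis |
| Responds, starts non-transplant therapy | Still at risk; a later relapse or death counts |
| Never responds, leaves with no listed reason recorded | No event |
| Never responds, alive and on study, no transplant | No event |

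The gap is the last two rows.

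**3. Size if EFS were estimated.** Let q be the share of patients who never respond, s the share of those alive and on study to Month 12 without transplant, and R the 12-month event-free share among responders.
- All non-responders counted as failures: EFS = R(1 − q).
- As worded, with stayers event-free: EFS = R(1 − q) + qs.
- Excess = qs.

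For illustration, take R = 0.59 and q = 1 − 0.81 = 0.19 from the earlier phase II study in Protocol 1.1.5.1; s is assumed.

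| q | s | Failures counted | As worded | Excess, points |
|---|---|---|---|---|
| 0.19 | 0.25 | 0.478 | 0.525 | 4.8 |
| 0.19 | 0.50 | 0.478 | 0.573 | 9.5 |
| 0.19 | 1.00 | 0.478 | 0.668 | 19 |
| 0.10 | 0.50 | 0.531 | 0.581 | 5 |
| 0.40 | 0.50 | 0.354 | 0.554 | 20 |

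Another route multiplies the share with active disease at entry (assumed 10%, 20% or 40%) by a non-response rate of 0.19, or of 2/3 from three re-infused children in Protocol 1.2, with everyone staying. It gives 1.9 to 6.7, 3.8 to 13.3 and 7.6 to 26.7 points. This is not an upper bound on the whole problem, because it leaves out patients who depart for an unlisted reason.

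**4. Size in this trial.** With at most 5 patients re-infused, moving one patient between event and no event shifts a simple proportion by at least 1/5 = 20 points. No EFS estimate would be informative under either definition, and none is planned. SAP 2.3.1, 2.4.3 and 2.9.1.1 list disposition with the main reason for discontinuation, later antineoplastic therapy and transplant, and deaths. A reader can follow each patient without an EFS derivation.

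**The case for a change.** The strongest case for a change is that the protocol wording is defective on its face and the SAP never corrects it. Making failure depend on disease status would cost little: the Day 28 marrow is mandatory and medications are recorded at visits. That case is right about the wording and the direction of the bias. It is also right that investigator decision, the one route in 9.1.1 by which a non-responder could be removed for lack of efficacy, leaves the event to discretion.

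Several supports are weaker.
- Patients who leave by their own or a guardian's decision are not all lost as events, because the recorded main reason may be one that 12.5.2 lists.
- The survival instruction, "Thus, patients should be followed-up for survival also in case of SCT", concerns overall survival after transplant. Those patients are already censored in the main EFS analysis, so it does not show that non-responders stay event-free.
- Following responders through new non-transplant therapy to relapse or death is a legitimate treatment-policy choice.
- Calling every patient without remission at Day 28 a failure dated to re-infusion would create a new conflict. Efficacy is assessed at months 1, 3, 6 and 12 (Protocol 3) and remission is judged over 12 months (Protocol 12.5.1). A remission first seen at Month 3 would be both a response and a failure at day 0.
- Protocol 8.3.1 relies on sponsor efficacy guidelines that are not reproduced; the Appendix 1 provided covers hepatitis serology. Whether those guidelines settle failure dates or censoring cannot be seen.

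**Conclusion.** The literal reading holds. Under Protocol 12.5.2, a patient with active leukemia who never responds, survives and stays on study without transplant has no EFS event. Had the trial run to plan, 12-month EFS would have been overstated by qs, roughly 5 to 19 points at 19% non-response with a quarter to all of the non-responders staying. Those inputs come from a first-infusion study and an assumed retention share, so they show scale only.

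No change follows because there is no gain. EFS was a descriptive secondary endpoint with no error control and no part in the sample size. SAP Amendment 2 cancels its analysis and reports listings for a trial that enrolled 5 patients. With the plan followed as it stands, no EFS estimate exists to be biased, and rewording the definition would change no reported result. This conclusion rests on the closeout plan being followed. The wording would matter again only if the definition were carried into another protocol or if an EFS figure were produced from these data.
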